1.1 Study Synopsis

Title: Boiled Peanut Oral Immunotherapy

Study Description: Prospective Phase 1 clinical trial providing proof of concept data on boiled peanut oral immunotherapy (OIT) for the treatment of peanut allergy in children. We hypothesize that the proportion of subjects successfully desensitized with boiled peanut OIT is greater than the theoretical placebo rate of 20%.

Objectives:

- Determine the effect of boiled peanut immunotherapy on the immune response to peanut.
- Compare the safety and tolerability of boiled peanut oral immunotherapy to published data on roasted peanut oral immunotherapy in pediatric subjects with confirmed IgE mediated peanut allergy.
- Primary endpoint: Response to treatment defined as ability to successfully consume a single dose of 300 mg or greater of peanut protein with no dose limiting symptoms at exit double blind placebo controlled food challenge (DBPCFC).
- Secondary endpoints:
- Maximum dose achieved with no or minimal symptoms at exit DBPCFC.
- Change in the maximum tolerated dose from screening to exit DBPCFC.
- The rate of side effects of treatment defined as oral itching, rhinorrhea, conjunctivitis, urticaria, angioedema, abdominal upset, vomiting, diarrhea, cough, wheeze, or anaphylaxis.
- Change in quality of life scores before and after treatment utilizing validated, age specific, food-related quality-of-life surveys before and after peanut oral immunotherapy (Supplement 1)
- Peanut protein component panel, to determine the presence of high levels of sensitivity to peanut proteins known to be associated with severe systemic reactions (Arah 1,2,3) versus mild reactions (Arah8).

Endpoints:

- Levels of peanut specific serum IgG4, with higher levels associated with increased tolerance to peanut protein.

Study Population:

Children ages 1-16 with peanut allergy suggested via history of reaction and objective evidence of IgE mediated hypersensitivity either via skin testing or in vitro testing (peanut specific IgE concentration) within the last 12 months.

Inclusion criteria:

[figure not shown]
- Age 1-16 years
- History of immediate hypersensitivity reaction to peanut or a high level of suspicion based on testing at the discretion of the investigator
- Evidence of IgE mediated peanut hypersensitivity within a 12 month period of study enrollment including:
 - Skin prick test with wheal diameter of at least 3mm and/or
 - Peanut specific IgE >0.35 ku/L

Exclusion criteria:

- History of life threatening peanut anaphylaxis
- Asthma requiring more than medium dose inhaled corticosteroids for age per the National Heart, Lung, and Blood Institute Asthma Guidelines
- Cardiovascular disease
- Use of beta-blockers (oral), angiotensin converting enzyme inhibitors, angiotensin receptor blockers, or calcium channel blockers
- Use of steroid medications in the following manners:
 - Daily oral steroid dosing for greater than 1 month during the past year OR
 - Burst or steroid course in the past 3 months before inclusion OR
 - Greater than 2 burst oral steroid courses in the past year of at least 1 week duration
- Pregnancy or lactation
- Prior participation in food oral immunotherapy studies, including OIT, sublingual immunotherapy (SLIT), or epicutaneous immunotherapy (EPIT)
- Eosinophilic gastrointestinal disease
- Oat allergy, as oat flour is the vehicle with which study drug may be mixed for purposes of blinding and will be used as placebo for the exit DBPCFC

	
• History of food protein-induced enterocolitis syndrome (FPIES)• History of developmental delay or speech delay that precludes age-appropriate communication, in the opinion of the investigator
Description of Sites and Facilities Enrolling Patients:	Screening will be performed at the Cleveland Clinic main campus and satellite outpatient clinic locations. Any patients identified as eligible will be referred to main campus for further evaluation and possible enrollment.
Description of Study Intervention:	Oral Immunotherapy will be administered utilizing a powder derived from boiled peanuts. Treatment will begin with an initial escalation day in which dosing is begun at 0.1 mg peanut protein and escalated to a final dose of 6 mg peanut protein. Doses are ingested orally. The subjects will continue daily oral ingestion of doses at home and return for updosing every 2 weeks to a final maintenance dose of 300 mg peanut protein. The subjects will continue daily oral ingestion of the peanut product for a minimum duration of 28 days before undergoing exit DBPCFC. At the conclusion of the study, patients will be offered continued maintenance therapy off study in line with current specialty standards.
Study Duration:	18 weeks
Participant Study Duration:	18 weeks

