1.2 Study Schema

1.3 Schedule of Activities

Procedures	Visit																			
	Enrollment/Baseline visit	Oral Food Challenge	Study Visit 1	Initial dose escalation	Study Visit 2 Visit 1 +1-4 weeks	Dose escalation visit 1	SV 3 Visit 2 +2 weeks	Dose Escalation Visit 2	SV 4 Visit 2 +4 weeks	Dose escalation visit 3	SV 5 Visit 2 +6 weeks	Dose escalation visit 4	SV 6 Visit 2 +8 weeks	Dose escalation visit 5	SV 7 Visit 2 +10 weeks	Dose escalation visit 6	SV 8 Visit 2 +12 weeks	Dose escalation visit 7	SV 9 Visit 2 +14 weeks	Oral Food Challenge
Informed Consent	X																			
Demographics	X																			
Vitals	X	X	X	X	X	X	X	X	X	X	X	X	X	X	X	X	X	X	X	
Spirometry*	X		X	X	X	X	X	X	X	X	X	X	X	X	X	X	X	X	X	
Blood Draw				X															X	
Skin prick test				X															X	
Oral food challenge		X																	X	
Urine Pregnancy	X																		X	
Study Drug Administration			X	X	X	X	X	X	X	X	X	X	X	X	X	X	X	X		
Study Drug Compliance					X	X	X	X	X	X	X	X	X	X	X	X	X	X	X	
AE Review			X	X	X	X	X	X	X	X	X	X	X	X	X	X	X	X	X	
Conmed Assessment	X	X	X	X	X	X	X	X	X	X	X	X	X	X	X	X	X	X	X	

FAQL Questionnaire	X										X
-----------------------	---	--	--	--	--	--	--	--	--	--	---

All dose escalation visits have a window of +/- 2 day

All follow up visits have a window of +/- 7 days

The enrollment/baseline visit, initial oral food challenge (SV 1), will take place at the Pediatric Allergy Clinic at the Cleveland Clinic main campus.

The initial escalation day, dose escalation visits, and final oral food challenge (SV 2-10) will take place in the Clinical Research Unit.

* Spirometry will be performed on all patients ages 5+ and/or at the physician's discretion at the initial study visit as well as the exit oral food challenge. Rather than full spirometry, peak flow will be performed at every updosing visit on all patients ages 4+ and/or if the physician feels that it is developmentally appropriate

2. Introduction

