+60 minutes	2 mg	Repeat vital signs. Examination of skin and auscultation of lungs prior to dose
+90 minutes	4 mg	Repeat vital signs. Examination of skin and auscultation of lungs prior to dose
+120 minutes	6 mg	Repeat vital signs. Examination of skin and auscultation of lungs prior to dose

*Vital signs including heart rate, blood pressure, respiratory rate and oxygen saturation level to be obtained with any change in physical exam or clinical status

Dose escalation will begin with 0.5 mg of peanut protein and increase to a maximum of 6 mg (Table 5). The doses will be administered at 30 minute intervals following a set of vital signs and limited physical examination. At any objective sign of reaction (Table 4) the escalation will stopped, and the patient will be treated based on the presenting symptoms and clinical judgment of the supervising investigator. Subjects will be monitored for 2 hours after resolution of any signs of reaction and/or after completion of the final dose.

Subjects will then be instructed to consume the highest tolerated dose of peanut protein daily until their return for dose escalation.

Build-Up

For the next phase, participants will undergo incremental dose escalations every two weeks. These dose escalations will take place under the supervision of a trained Allergy/Immunology physician investigator within the Clinical Research Unit. The subject will be given an increased dose of the peanut and observed for at least 2 hours. Subjects will then continue to take daily doses of an identical amount of peanut protein at home. We will increase to a target maintenance dose of 300 mg of peanut protein, which should be accomplished in approximately 6 dose increases, or 12 weeks' time.

If a patient is unable to tolerate the maximum dose during the initial dose escalation visit, they will be given double the maximum dose tolerated during the dose escalation visits until they are back on the dose escalation schedule defined in Table 6.

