If a subject does not tolerate a dose increase, then the patient will be administered a dose reduced by 25%, with increase to the originally intended dose at the subsequent visit. If the patient still does not tolerate the dose, then the decision on how to proceed will be determined at the investigator's discretion. This may involve temporarily decreasing the subject's dose, making a smaller increase, or prolonging the duration of a given dose. If any subject is unable to reach the goal maintenance dose, then the investigator may decide to continue the subject on a lower maintenance dose for the duration of the study.

Table 6: Dose Escalation Schedule

Dose of Peanut Protein	Week of Protocol
6 mg	0
12 mg	2
25 mg	4
50 mg	6
75 mg	8
150 mg	10
300 mg	12

Home Dosing

All subjects will be offered the opportunity to continue once daily consumption of the maintenance dose after the end of their study participation. This ongoing maintenance therapy is optional and will not be paid for by the study. The subjects will be instructed to otherwise continue a peanut free diet.

Follow Up

The subject will also undergo a final oral food challenge at the final visit (SV10). This food challenge will be double blind and placebo controlled. A double blind placebo controlled food challenge (DBPCFC) is the gold standard for diagnosis of food allergy and is the standard utilized for most oral immunotherapy trials at exit.

Roasted peanut powder will be utilized for the challenge, with oat flour as placebo. An individual will undergo a standard challenge described below (Table 7) with either the roasted peanut or the placebo, blinded to both subject and investigators. The same individual will then undergo a second challenge with the opposite (either peanut or placebo) either later that day or by returning to clinic the following day. Each challenge will be performed by increasing doses up to a final dose of 1000 mg of peanut protein. The individual doses will be 25, 100, 200, 300, 600, and 1000 mg of peanut protein. The highest tolerated dose will be recorded. If a patient reacted to a dose lower than 25 mg of peanut powder during the initial Oral Food Challenge then they will be started at the dose lower than where the reaction occurred for the DBOFC.

A urine pregnancy test will be repeated on all females of child bearing potential before the DBOFC.

Table 7: Double blind oral food challenge to peanut or control oat (SV 10)

Time	Dose	Clinician Intervention *

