7.1 Discontinuation of Study Intervention

Criteria for discontinuing oral immunotherapy in a subject will include:

- Subject nonadherence to OIT, specifically defined by 12 (approximately 10%) nonconsecutive missed doses.
- A life-threatening adverse reaction to OIT, specifically a grade 4 reaction as defined by the Consortium of Food Allergy Research (CoFAR) criteria. See table in Section 8.3.3.1.
- Symptoms suggestive of Eosinophilic Esophagitis (EoE) – i.e. difficulty swallowing, chest pain, persistent heart burn, upper abdominal pain, and/or no response to gastroesophageal reflux disease (GERD) medication

Symptoms suggestive of Eosinophilic Esophagitis (EoE) will prompt discontinuation of oral immunotherapy and begin once weekly symptom monitoring phone calls with study staff. If symptoms fail to resolve after 1 month off therapy, consultation with Gastroenterology will be considered for further evaluation and management.

Discontinuation from oral immunotherapy does not mean discontinuation from the study, and remaining study procedures should be completed as indicated by the study protocol. If a clinically significant finding is identified (including, but not limited to changes from baseline) after enrollment, the investigator or qualified designee will determine if any change in participant management is needed. Any new clinically relevant finding will be reported as an adverse event (AE).

The data to be collected at the time of study intervention discontinuation will include the following:

- Skin prick test to peanut
- Peanut sIgE, peanut component panel, and peanut IgG4

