6.3 Study Assessments

The study Schedule of Activities as provided in section 1.3 of the protocol is as follows.

Visit		Study Visit 1	Study Visit 2 Visit 1 +1-4 weeks	SV 3 Visit 2 +2 weeks	SV 4 Visit 2 +4 weeks	SV 5 Visit 2 +6 weeks	SV 6 Visit 2 +8 weeks	SV 7 Visit 2 +10 weeks	SV 8 Visit 2 +12 weeks	SV 9 Visit 2 +14 weeks	SV 10 Visit 1 +18 weeks

Procedures		Enrollment/Baseline visit	Oral Food Challenge	Initial dose escalation	Dose escalation visit 1	Dose Escalation Visit 2	Dose escalation visit 3	Dose escalation visit 4	Dose escalation visit 5	Dose escalation visit 6	Dose escalation visit 7	Oral Food Challenge
Informed Consent	X											
Demographic s	X											
Vitals	X	X	X	X	X	X	X	X	X	X	X	X
Spirometry*	X		X	X	X	X	X	X	X	X	X	X
Blood Draw			X									X
Skin prick test			X									X
Oral food challenge		X										X
Urine Pregnancy	X											X
Study Drug Administratio n			X	X	X	X	X	X	X	X	X	
Study Drug Compliance				X	X							
AE Review			X	X	X	X	X	X	X	X	X	X
Conmed Assessment	X	X	X	X	X	X	X	X	X	X	X	X
FAQL Questionnaire	X											X

Due to the difficulties of scheduling study visits during the COVID-19 pandemic, the primary analysis will not place any limitations on the timing of study visits. All study visits will be analyzed in order by date, and the number of days from initial oral food challenge (OFC) and initial dose escalation visit will be reported for each study visit. If more than seven dose escalation visits are required as described in the study protocol section 6.1.1 'Study Intervention Description', the additional study visits will be named 'Additional Study Visit 9.1' through 'Additional Study Visit 9.x' for the purposes of analysis and reporting.

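### The exit challenge is timed from Visit 1 but build-up from Visit 2, so the schedule does not secure the 28-day minimum before the primary-endpoint challenge

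*Protocol*

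**What the plan says.** **The minimum.** The synopsis (Protocol 1.1, Description of Study Intervention) describes two-weekly updosing to a final maintenance dose of 300 mg. The next sentence is "The subjects will continue daily oral ingestion of the peanut product for a minimum duration of 28 days before undergoing exit DBPCFC". Section 6.1.2, which describes the exit challenge under Follow Up, does not repeat the 28 days.

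**The schedule.** Protocol 1.3 gives "Study Visit 2 Visit 1 +1-4 weeks" and counts SV3 to SV9 from Visit 2, with SV8 at 12 weeks and SV9 at 14 weeks. The heading of the exit-challenge column is legible only in SAP 6.3, where it reads "SV 10 Visit 1 +18 weeks". The SAP introduces that table with "The study Schedule of Activities as provided in section 1.3 of the protocol is as follows". Both duration lines in the synopsis say 18 weeks.

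**Windows.** Escalation visits have 2 days either way. For the rest, Protocol 1.3 says "All follow up visits have a window of +/- 7 days".

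**Build-up.** Table 6 in Protocol 6.1.2 starts at 6 mg in week 0 and reaches 300 mg in week 12. A child who cannot take the full first-day dose is given "double the maximum dose tolerated during the dose escalation visits until they are back on the dose escalation schedule". A child who fails an increase is "administered a dose reduced by 25%, with increase to the originally intended dose at the subsequent visit". The investigator may settle on a lower maintenance dose.

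**The analysis.** SAP 6.3 places no limits on visit timing, citing COVID-19, and names additional visits 9.1 to 9.x where build-up runs long. The Efficacy Population (SAP 8.2.2) requires both challenges but no minimum time at maintenance.

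**The concern.** Two rules govern when the primary-endpoint challenge takes place, and they use different clocks. The 28-day minimum runs from the maintenance dose, which is reached a set number of weeks after Visit 2. SV10 runs from Visit 1. Every week between Visits 1 and 2 therefore comes off the time at maintenance.

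A site that keeps to the schedule would challenge some children after less maintenance than the synopsis requires. A site that keeps to the minimum would, for some children, have to hold SV10 later than its window allows. Different handling would make time at maintenance vary from child to child without anyone having planned it.

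SV10 yields the primary endpoint. With 10 children, each response is worth 10 percentage points, and a child who does not tolerate 300 mg or does not complete the challenge counts as a non-responder (SAP 9.2.1). The primary objective also looks to published results with roasted peanut, and Protocol 4.2 describes the phases as comparable with those studies in duration.

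**Working it through.** **Inputs**

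- Visit 2: *g* = 1, 2, 3 or 4 weeks after Visit 1 (Protocol 1.3).
- SV10: Visit 1 + 18 weeks = day 126 (SAP 6.3).
- First 300 mg dose, 6 mg start, no failed increase: 6, 12, 25, 50, 75, 150, 300 is 6 increases at 2-week intervals, so 12 weeks after Visit 2, which is SV8. This matches Table 6.
- First 300 mg dose, 4 mg start: 4, 8, 12, 25, 50, 75, 150, 300 is 7 increases, so 14 weeks, which is SV9. Rejoining through 6 mg instead of 8 mg gives the same count.
- First 300 mg dose, 6 mg start with one failed increase: 12 + 2 = 14 weeks, also SV9.
- Windows: 2 days either way for SV8 and SV9; 7 days either way for SV10, taking it to be a follow-up visit.

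**Formula**

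Days at 300 mg by nominal SV10 = 126 − 7*g* − 7*w*, where *w* is the number of weeks from Visit 2 to the first 300 mg dose. The windows widen this by 7 + 2 = 9 days in each direction.

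**Results with SV10 at Visit 1 + 18 weeks**

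| Visit 2 at week | 300 mg at SV8 (*w* = 12): nominal | with windows | 300 mg at SV9 (*w* = 14): nominal | most with windows |
|---|---|---|---|---|
| 1 | 126 − 7 − 84 = 35 | 26 to 44 | 126 − 7 − 98 = 21 | 30 |
| 2 | 126 − 14 − 84 = 28 | 19 to 37 | 126 − 14 − 98 = 14 | 23 |
| 3 | 126 − 21 − 84 = 21 | 12 to 30 | 126 − 21 − 98 = 7 | 16 |
| 4 | 126 − 28 − 84 = 14 | 5 to 23 | 126 − 28 − 98 = 0 | 9 |

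For the uncomplicated 6 mg starter, the nominal schedule gives 28 days only if Visit 2 is at most 126 − 84 − 28 = 14 days after Visit 1. With every window used in the child's favour, the limit is 14 + 9 = 23 days. A 4-week gap therefore always falls short. At that gap SV9 (Visit 1 + 4 + 14 = 18 weeks) and SV10 also fall in the same week.

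For a child who first reaches 300 mg at SV9, the nominal schedule never gives 28 days. Favourable windows give it only with Visit 2 at week 1.

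**If SV10 were meant to be Visit 2 + 18 weeks**

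- After SV8: 126 − 84 = 42 days nominal, 42 − 9 = 33 at the worst windows, whatever the Visit 2 gap.
- After SV9: 126 − 98 = 28 days nominal, but 28 − 9 = 19 at the worst windows.

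That anchor would protect the uncomplicated child but not the one who arrives at SV9.

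**The case against.** **The 28 days could mean any dose.** The sentence refers to the peanut product and does not repeat 300 mg. Read that way it is always met, because Visit 2 to SV10 is 18 − 4 = 14 to 18 − 1 = 17 weeks. But a minimum that no child could miss would do nothing, and the sentence directly follows the maintenance dose. The maintenance reading is the natural one, though it remains a reading.

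**The anchor may be a slip.** It rests on one column heading, every build-up visit is counted from Visit 2, and Visit 2 + 18 weeks would be exactly 28 days after SV9. This is plausible, and the 18-week duration lines do not settle it. It would still need correcting, and the substitute anchor does not secure the minimum after SV9.

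**Sites can delay SV10.** SAP 6.3 attaches no penalty to a late visit and foresees extra escalation visits. This stands, but the same text accepts an early SV10 just as readily.

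**The consequence may be small.** The endpoint definition has no maintenance-duration condition, and the documents give no evidence that 14 rather than 28 days changes tolerance of 300 mg. Visit timing and dose by visit are already to be tabulated (SAP Tables 1.4 and 4.1), so time at maintenance could be derived. This stands, and it keeps the point minor.

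**Stronger readings that the documents do not support.**

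- A reader might infer that a child starting at 2 mg can never meet the minimum. That holds SV10 at week 18 while escalation is still running, whereas the SAP provides visits 9.1 to 9.x without timing limits.
- A reader might infer that meeting the minimum always pushes SV10 out of its window. An uncomplicated 6 mg starter with Visit 2 at weeks 1 to 3 can comply within it.
- A reader might take two short timings out of four to mean half the children. The documents give no distribution of Visit 2 timings.

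**Conclusion.** The point holds as a minor internal inconsistency: the stated schedule does not deliver a stated minimum before the primary-endpoint challenge. For the most straightforward child, time at 300 mg by nominal SV10 is 35, 28, 21 or 14 days according to when Visit 2 falls. With Visit 2 at week 4 no permitted use of the windows reaches 28. For a child who first reaches 300 mg at SV9 the figures are 21, 14, 7 or 0 days if SV10 stays at week 18.

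This rests on three assumptions: the 28 days are counted at maintenance, the SAP copy of the SV10 heading reflects the protocol, and SV10 carries the 7-day follow-up window.

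The number of children affected among the 10 is unknown. Shorter maintenance is unlikely to make 300 mg easier to tolerate, so any bias in the response rate is likely to be against the treatment. It would be wrong to conclude that the primary test is invalid or that a positive result would be inflated; nothing in the documents supports either.

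**What to change.** 1. In Protocol 1.3 and its copy in SAP 6.3, replace "SV 10 Visit 1 +18 weeks" with: at least 28 days after the first dose at 300 mg, or at the lower maintenance dose set by the investigator; window 0 to +7 days. Moving the anchor to Visit 2 alone is not enough, for the reason shown in the working.
2. Keep a calendar-based SV10 for children who stop dosing but remain in the study, since Protocol 7.1 says "Discontinuation from oral immunotherapy does not mean discontinuation from the study" and the new rule would otherwise give some of them no date.
3. Repeat the 28 days in Protocol 6.1.2 under Follow Up.
4. Change the two 18-week duration lines in the synopsis to a variable duration: about 17 weeks or more from Visit 1 (1 + 12 + 4 at the shortest), depending on Visit 2 timing and delayed increases.
5. Add to SAP Table 1.4 the days from first maintenance dose to SV10. For any child who has already had the exit challenge, this is the part that still helps, and it needs no new data.

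The cost is two table headings, a few sentences and one table column. The primary test and sample size do not change. The downside is longer and more variable participation for some children, with the extra dosing and product supply that this brings.

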1.2 Study Schema

1.3 Schedule of Activities

Procedures	Visit																			
	Enrollment/Baseline visit	Oral Food Challenge	Study Visit 1	Initial dose escalation	Study Visit 2 Visit 1 +1-4 weeks	Dose escalation visit 1	SV 3 Visit 2 +2 weeks	Dose Escalation Visit 2	SV 4 Visit 2 +4 weeks	Dose escalation visit 3	SV 5 Visit 2 +6 weeks	Dose escalation visit 4	SV 6 Visit 2 +8 weeks	Dose escalation visit 5	SV 7 Visit 2 +10 weeks	Dose escalation visit 6	SV 8 Visit 2 +12 weeks	Dose escalation visit 7	SV 9 Visit 2 +14 weeks	Oral Food Challenge
Informed Consent	X																			
Demographics	X																			
Vitals	X	X	X	X	X	X	X	X	X	X	X	X	X	X	X	X	X	X	X	
Spirometry*	X		X	X	X	X	X	X	X	X	X	X	X	X	X	X	X	X	X	
Blood Draw				X															X	
Skin prick test				X															X	
Oral food challenge		X																	X	
Urine Pregnancy	X																		X	
Study Drug Administration			X	X	X	X	X	X	X	X	X	X	X	X	X	X	X	X		
Study Drug Compliance					X	X	X	X	X	X	X	X	X	X	X	X	X	X	X	
AE Review			X	X	X	X	X	X	X	X	X	X	X	X	X	X	X	X	X	
Conmed Assessment	X	X	X	X	X	X	X	X	X	X	X	X	X	X	X	X	X	X	X	

FAQL Questionnaire	X										X
-----------------------	---	--	--	--	--	--	--	--	--	--	---

All dose escalation visits have a window of +/- 2 day

All follow up visits have a window of +/- 7 days

The enrollment/baseline visit, initial oral food challenge (SV 1), will take place at the Pediatric Allergy Clinic at the Cleveland Clinic main campus.

The initial escalation day, dose escalation visits, and final oral food challenge (SV 2-10) will take place in the Clinical Research Unit.

* Spirometry will be performed on all patients ages 5+ and/or at the physician's discretion at the initial study visit as well as the exit oral food challenge. Rather than full spirometry, peak flow will be performed at every updosing visit on all patients ages 4+ and/or if the physician feels that it is developmentally appropriate

2. Introduction

